8. RESEARCH METHODS

8.1. Study Design

This is a prospective, non-interventional (NI), multicenter study being conducted in Africa Middle East (AfME) countries. The aim is to understand palbociclib treatment patterns, clinical outcomes and QoL for patients with metastatic/locally advanced BC being treated in routine clinical practice in 7 AfME countries: Egypt, Jordan, KSA, Lebanon, Morocco, Qatar and UAE.

Approximately 200 patients from 19 centers across the 7 countries will be enrolled. The recruitment period (ie, from first patient into last patient in) will span over 18 months.

[figure not shown]
Patients will be enrolled at the time of treatment initiation with palbociclib and will be followed up over a 24-month period at time intervals per routine care, or until patient's withdrawal from the study or death (whichever comes first). Prospective data on clinical characteristics, treatment patterns, clinical outcomes and QoL will be collected ([Figure 1](#)).

Participation in this study is not intended to change the routine treatment patients receive, as determined by their prescribing physicians; all treatment decisions, type and timing of the disease monitoring are per routine clinical care, and at the discretion of treating physician and patient.

All assessments described in this protocol are performed as part of normal clinical practice or standard practice guidelines for the patient population and healthcare provider specialty in the countries where this non-interventional study is being conducted.

All assessments described in this protocol are performed as part of normal clinical practice or standard practice guidelines for the patient population and healthcare provider specialty in the countries where this non-interventional study is being conducted.

Figure 1. Study Design

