2.1. Study Design

This is a prospective, non-interventional (NI), multicentre study being conducted in Africa Middle East (AfME) countries. The aim is to understand palbociclib treatment patterns, clinical outcomes and QoL of patients with metastatic/locally advanced BC being treated in routine clinical practice in seven AfME countries: Egypt, Jordan, Lebanon, UAE, Qatar, Morocco and KSA.

Participation in this study is not intended to change the routine treatment patients receive, as determined by their prescribing physicians; all treatment decisions, type and timing of the disease monitoring are per routine clinical care, and at the discretion of the treating physician and patient.

Study population

[figure not shown]
Patients with HR+/HER2- metastatic/locally advanced BC within Egypt, Jordan, Lebanon, UAE, Qatar, Morocco and KSA will be enrolled from a geographically representative population as well as from diverse treatment settings (eg, academic and community sites). Patients whose treatment decision with palbociclib combination has been made by their treating physician and meet the eligibility criteria will be invited to participate in the study in a consecutive manner and over 12 months of recruitment.

Approximately 350-410 patients from 19 centers across the seven countries will be enrolled. The recruitment period (ie, from first patient in to last patient in) will span over 12 months.

Patients will be enrolled at the time of treatment initiation with palbociclib, and will be followed up over a maximum of 24-month period at time intervals per routine care, or until the end of Palbociclib treatment, progression or patients' withdrawal from the study (whichever comes first). Eligibility will be assessed at the date of the enrollment.

Prospective data on clinical characteristics, treatments patterns, clinical outcomes and QoL will be collected in accordance with routine standard of care visits (Figure 1). Data will be collected at enrollment (time of treatment initiation), during treatment with Palbociclib (at time intervals per routine care) and after treatment with palbociclib. After the end of treatment with palbociclib, data related to the first immediate subsequent treatment received will be collected.

Figure 1. Study Design

FPI: first patient in; LPI: last patient in; LPO: last patient out; QoL: quality of life

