- *Combination therapy (ie, palbociclib plus letrozole/aromatase inhibitor, palbociclib plus fulvestrant).* The combination of therapies will be determined at the Palbociclib treatment initiation. Palbociclib plus letrozole/aromatase inhibitor group will be defined as patients receiving Palbociclib and either Anastrozole, Letrozole or Exemastane. Palbociclib plus fulvestrant group will be defined as patients receiving Palbociclib and Fulvestrant. Other endocrine therapies will not be considered in this definition. Descriptive summary tables for the subgroup analysis by combination therapy line for the specified study objectives will be created as shown in [Table Shells 3, 15, 23, 31, 39, 46, 55, 63](#).
- *Line of therapy (1st or 2nd).* Line of therapy will be determined at the Palbociclib treatment initiation and defined as whether Palbociclib has been used as the first or second line endocrine therapy for metastatic/locally advanced BC. Descriptive summary tables for the subgroup analysis by combination therapy line for the specified study objectives will be created as shown in [Table Shells 4, 16, 24, 32, 40, 48, 56, 64](#).

- *Country (Egypt, Jordan, Lebanon, UAE, Qatar, Morocco and KSA).* Descriptive summary tables for subgroup analysis by country for the specified study objectives will be created as shown in Table Shells 5, 17, 25, 33, 41, 49, 57, 65.
- *Menopausal status (premenopausal vs. postmenopausal).* Menopausal status will be assessed at the Palbociclib treatment initiation. Descriptive summary tables for the subgroup analysis by menopausal status for the specified study objectives will be created as shown in Table Shells 6, 18, 26, 34, 42, 50, 58, 66.
- *Metastatic status (de novo vs. recurrent disease)* The recurrence of the disease will be assessed at the Palbociclib treatment initiation. Descriptive summary tables for the subgroup analysis by disease recurrence for the specified study objectives will be created as shown in Table Shells 7, 19, 27, 35, 43, 51, 59, 67.

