- *Metastatic site (visceral vs. non-visceral).* Visceral metastases refers to lung, liver, brain, pleural, and peritoneal involvement. Metastatic site will be defined according to the baseline lesion data. Visceral metastases will refer to lung, liver, brain, pleural, and peritoneal involvement. Non-visceral metastases include lesions in bone and skin/soft tissues. Lesions in lymph nodes will be categorised to neither of the groups. Lesions in bone may also be categorised to bone-only category. Descriptive summary tables will be presented as shown in Table Shells 8, 20, 28, 36, 44, 52, 60, 68.
- *Age (<55, 55-64, ≥65).* The age of the patient will be determined at the Palbociclib treatment initiation. Descriptive summary tables for the subgroup analysis by age for the specified study objectives will be created as shown in Table Shells 9, 21, 29, 37, 45, 53, 61, 69.

Additional stratifications can be conducted by eg, ECOG performance (stratified into groups 0-5), endocrine sensitivity vs. endocrine resistance (primary and secondary), if relevant and/or enough data are available.

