- 090177e1990673e39a54dc25f1a9a15read On: 28-Feb-2023 09:56 (GMT)

9. ANNEX 1

Table 3. Study Variables

Variable	Role	Time point(s)	Data source(s)	Operational definition
Age, continuous	Demographics (secondary endpoint)	At initial diagnosis of BC At the initiation of Palbociclib treatment	CRF sheets: Early Breast Cancer medical History, Palbociclib treatment initiation	Age will be reported in years (YY)
Age, categorical	Stratification variable	At the initiation of Palbociclib treatment	CRF sheet: Palbociclib treatment initiation	Two variables, age categorized into the following groups: 
 <55 years or >=55 years <65 years or >=65 years
Year of initiation of Palbociclib treatment	Demographics (secondary endpoint)	At the initiation of Palbociclib treatment	Palbociclib Treatment Initiation	Year of initiation of Palbociclib treatment
Time since initial diagnosis of breast cancer (days)	Demographics (secondary endpoint)	At the initiation of Palbociclib treatment	Palbociclib Treatment Initiation	Date of initiation of Palbociclib treatment – date of initial diagnosis of BC
Gender	Demographics (secondary endpoint)	At the initiation of Palbociclib treatment	CRF sheet: Demographic Characteristics	Gender (sex) is defined as: 
Male
 
Female

Country	Demographics (secondary endpoint), stratification variable	At the initiation of Palbociclib treatment	CRF sheet: Demographic Characteristics	There are nine countries in the study: 
Egypt
 
Jordan
 
Lebanon
 
UAE (United Arab Emirates)
 
Qatar
 
Morocco
 
KSA (Kingdom of Saudi Arabia)

Ethnicity	Demographics (secondary endpoint)	At the initiation of Palbociclib treatment	CRF sheet: Demographic Characteristics	There are nine ethnic groups: 
 Middle Eastern Caucasian / White Black Hispanic Native American Asian / Pacific Islander Australian / South European Australian (Aboriginal) Unknown

PFIZER CONFIDENTIAL

Variable	Role	Time point(s)	Data source(s)	Operational definition
				
 Other
Insurance	Demographics (secondary endpoint)	At the initiation of Palbociclib treatment	CRF sheet: Demographic Characteristics	There are two insurance types: 
 Public Private
Weight	Demographics (secondary endpoint)	At the initiation of Palbociclib treatment	CRF sheet: Demographic Characteristics	Weight will be reported in kilograms (kg).

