Number of patients with lesions	Clinical characteristics (secondary endpoint)	At diagnosis of advanced/metastatic BC	CRF sheet: Palbociclib Baseline Tumor Assessment	
Number of patients with lesions according to site. Sites of lesions are categorized as:
 
 Brain (visceral) Lung/pleura (visceral) Liver (visceral) Bone (non-visceral/bone-only) Breast/chest wall (non-visceral) Lymph nodes (none) Skin/soft tissue (non-visceral) Ovary (non-visceral) Other (e.g. peritoneal (visceral))
ECOG performance	Clinical characteristics (secondary endpoint)	At diagnosis of advanced/metastatic BC	CRF sheet: Palbociclib Baseline Tumor Assessment	
ECOG status will be categorised as
 
 0: Fully active, able to carry on all pre-disease performance without restriction 1: Restricted in physically strenuous activity but ambulatory and able to carry out work of a light or sedentary nature, e.g. light housework, office work 2: Ambulatory and capable of all self-care but unable to carry out any work activities. Up and about 50% of waking hours 3: Capable of only limited self-care, confined to bed or chair more than 50% of waking hours 4: Completely disabled, cannot carry on any self-care. Totally confined to bed or chair. 5: Dead

PFIZER CONFIDENTIAL

CT24-WI-GL03-RF02 2.0 Non-Interventional Statistical Analysis Plan For Primary Data Collection Study 01-Jun-2020

Variable	Role	Time point(s)	Data source(s)	Operational definition
Overall tumor response	Clinical outcomes (primary endpoint)	At follow-up visits	CRF sheet: Tumor Assessment form	
Overall tumor response will be categorised as:
 
 Progressive disease, defined as an increase in visible disease and/Or presence of any new lesions, including cases where the clinician indicates progressive disease Complete response, defined as complete reduction of all visible disease Partial response, defined as partial reduction in size of visible disease in some or all areas without any areas of increase in visible disease Stable disease, defined as no change in overall size of visible disease, also including cases where some lesions increased in size and some lesions decreased in size

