Min, max	xx.x, xx.x
Missing	XX (xx%)
Sex	
Female	XX (xx%)
Country	
Algeria	XX (xx%)
Egypt	XX (xx%)
KSA	XX (xx%)
Kuwait	XX (xx%)
Lebanon	XX (xx%)
Morocco	XX (xx%)
UAE	XX (xx%)
Missing	XX (xx%)
Ethnicity	
Middle Eastern	XX (xx%)
Caucasian / White	XX (xx%)
Black	XX (xx%)
Hispanic	XX (xx%)
Native American	XX (xx%)
Asian / Pacific Islander	XX (xx%)
Australian / South European	XX (xx%)
Australian (Aboriginal)	XX (xx%)
Unknown	XX (xx%)
Other	XX (xx%)
Missing	XX (xx%)
Insurance type	
Public	XX (xx%)
Private	XX (xx%)
Missing	XX (xx%)
Family history of breast cancer	
Yes	XX (xx%)

PFIZER CONFIDENTIAL

CT24-WI-GL03-RF02 2.0 Non-Interventional Statistical Analysis Plan For Primary Data Collection Study 01-Jun-2020

Page 56 of 172

0901776099673e30A5481150.pdf Printed On: 28-Feb-2023 09:56 (GMT)

Table Shell 10 - Descriptive summary table of the *demographic and initial clinical* profiles of BC patients who have received Palbociclib treatment as *first line therapy for metastatic/locally advanced BC*.

No	XX (xx%)
Missing	XX (xx%)
Smoking habits	
Current smoker	XX (xx%)
Ex-smoker	XX (xx%)
Non-smoker	XX (xx%)
Unknown	XX (xx%)
Missing	XX (xx%)
Age at menarche [year]	
Number of females	
Mean (SD)	XX (xx%)
Q1, median, Q3	XX (xx%)
Min, max	XX (xx%)
Missing	XX (xx%)
Age at menopause [year]	
Number of females	XX (xx%)
Mean (SD)	xx.x (xx.x)
Q1, median, Q3	xx.x, xx.x, xx.x
Min, max	xx.x, xx.x
Missing	XX (xx%)
Number of children	
Number of female patients having children	XX (xx%)
Mean (SD)	xx.x (xx.x)
Q1, median, Q3	xx.x, xx.x, xx.x
Min, max	xx.x, xx.x
Missing	XX (xx%)
History of breast feeding	
Yes	XX (xx%)
No	XX (xx%)
Missing	XX (xx%)
Clinical stage of early BC	
I	XX (xx%)
IIA	XX (xx%)
IIB	XX (xx%)
IIIA	XX (xx%)
IIIB	XX (xx%)
IIIC	XX (xx%)
Missing	XX (xx%)
Pathological stage of early BC	

090177e1990673e39a54de25f1famp5ivred On: 28-Feb-2023 09:56 (GMT)

090177e1990673e39a54de25f1famp5ivred On: 28-Feb-2023 09:56 (GMT)

090177e1990673e39a54de25f1famp5ivred On: 28-Feb-2023 09:56 (GMT)

090177e1990673e39a54de25f1famp5ivred On: 28-Feb-2023 09:56 (GMT)

Table Shell 10 - Descriptive summary table of the *demographic and initial clinical* profiles of BC patients who have received Palbociclib treatment as first line therapy for metastatic/locally advanced BC.

Papillary carcinoma	XX (xx%)
Metaplastic breast cancer (MBC)	XX (xx%)
Phyllodes carcinoma	XX (xx%)
Mammary Paget disease (MPD)	XX (xx%)
Inflammatory breast cancer	XX (xx%)
Other	XX (xx%)
Missing	

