Number of patients with lesions in brain	XX (xx%)
Number of patients with lesions in lung/pleura	XX (xx%)
Number of patients with lesions in liver	XX (xx%)
Number of patients with lesions in bone	XX (xx%)
Number of patients with lesions in breast/chest wall	XX (xx%)
Number of patients with lesions in lymph nodes	XX (xx%)
Number of patients with lesions in skin/soft tissue	XX (xx%)
Number of patients with lesions in ovary	XX (xx%)
Number of patients with lesions in other site	XX (xx%)
ECOG performance	
0	XX (xx%)
1	XX (xx%)
3	XX (xx%)
4	XX (xx%)
5	XX (xx%)
Not documented	XX (xx%)
Missing	XX (xx%)
Endocrine sensitivity	
Endocrine therapy naïve	XX (xx%)
Endocrine sensitive	XX (xx%)
Primary endocrine resistant	XX (xx%)
Secondary endocrine resistant	XX (xx%)
Not applicable	XX (xx%)
Missing	XX (xx%)
Comorbidities	
[disease/comorbidity 1]	XX (xx%)

PFIZER CONFIDENTIAL

090177a099673e39a54dc25f1famp15reed On: 28-Mar-2023 09:56 (GMT)

090177a099673e39a54dc25f1famp15reed On: 28-Mar-2023 09:56 (GMT)

Table Shell 13 - Descriptive summary table of the *clinical* profiles of BC patients at the initiation of Palbociclib treatment as second line therapy for metastatic/locally advanced BC.

Variable	Summary statistics
Number of patients who have received palbociclib combination treatment in line with locally approved indications	XX
Year of initiation of Palbociclib treatment	
2020	XX (xx%)
2021	XX (xx%)
2022	XX (xx%)
2023	XX (xx%)
...	...
Time from initial diagnosis of breast cancer to Palbociclib treatment initiation [days]	
N	XX (xx%)
Mean (SD)	xx.x (xx.x)
Q1, median, Q3	xx.x, xx.x, xx.x
Min, max	xx.x, xx.x
Missing	XX (xx%)
Time from initial diagnosis of breast cancer to recurrence [days]	
N	XX (xx%)
Mean (SD)	xx.x (xx.x)
Q1, median, Q3	xx.x, xx.x, xx.x
Min, max	xx.x, xx.x
Missing	XX (xx%)
Age at baseline [year]	
N	XX (xx%)
Mean (SD)	xx.x (xx.x)
Q1, median, Q3	xx.x, xx.x, xx.x
Min, max	xx.x, xx.x
Missing	XX (xx%)
Weight [kg]	
N	XX (xx%)
Mean (SD)	xx.x (xx.x)
Q1, median, Q3	xx.x, xx.x, xx.x
Min, max	xx.x, xx.x
Missing	XX (xx%)
Height [m]	
N	XX (xx%)
Mean (SD)	xx.x (xx.x)
Q1, median, Q3	xx.x, xx.x, xx.x
Min, max	xx.x, xx.x
Missing	XX (xx%)
BMI [kg/m²]	
N	XX (xx%)

Table Shell 13 - Descriptive summary table of the *clinical* profiles of BC patients at the initiation of Palbociclib treatment as second line therapy for metastatic/locally advanced BC.

Mean (SD)	xx.x (xx.x)
Q1, median, Q3	xx.x, xx.x, xx.x
Min, max	xx.x, xx.x
Missing	XX (xx%)
BMI category	

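### The baseline table shells contradict the SAP's own variable definitions: two wrong countries, two study countries left out, no ECOG 2 row and no row for men

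*SAP*

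**What the plan says.** **Country.** Protocol section 8.1 names "7 AfME countries: Egypt, Jordan, KSA, Lebanon, Morocco, Qatar and UAE". SAP section 2.1 agrees: "seven AfME countries: Egypt, Jordan, Lebanon, UAE, Qatar, Morocco and KSA". The country stratum in SAP section 3.2 has the same set: "Egypt, Jordan, Lebanon, UAE, Qatar, Morocco and KSA". In SAP Annex 1, Table 3, the Country variable opens with "There are nine countries in the study" and then lists those same seven. The Country block of Table Shell 10 (first-line patients) runs "Algeria XX (xx%) Egypt XX (xx%) KSA XX (xx%) Kuwait XX (xx%) Lebanon XX (xx%) Morocco XX (xx%) UAE XX (xx", followed by a Missing row. Shell 11 (second-line patients) is identical. Neither has a row for Jordan, Qatar or other countries.

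**ECOG.** Annex 1 defines six grades, including "2: Ambulatory and capable of all self-care but unable to carry out any work activities". SAP section 3.2 offers an optional stratification by "ECOG performance (stratified into groups 0-5"). The block headed "ECOG performance" in Shells 12 and 13 has rows for 0, 1, 3, 4, 5, not documented and missing.

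**Sex.** Annex 1 codes gender as male or female. The Sex block of Shells 10 and 11 has one row, Female, and no Missing row.

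The eligibility criteria (Protocol 8.2.1 and 8.2.2; SAP 2.1.1 and 2.1.2) set no limit on sex or ECOG grade. SAP section 6.2 assigns the demographic and clinical description to Shells 10 to 13.

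**The concern.** Describing who was enrolled is a secondary objective, and Protocol section 6.2 justifies the study partly on the ground that trial populations may not represent the patients treated in practice. Shells 10 to 13 are the tables meant to deliver that description, and SAP section 3.2 does not include it among the objectives to be tabulated by subgroup.

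A shell is an instruction to the programmer. If a recorded value has no row, the patient is either left unclassified, so that the block does not add up, or counted as missing. The second outcome matters because Protocol section 8.7 and SAP section 5 promise to report the amount of missing data. Recorded values filed as missing would distort that figure.

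**Working it through.** No formula in the plan is at issue, so the check compares category lists and then counts planned patients.

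**1. Planned numbers (Protocol section 8.5, Table 3).** Patients: Egypt 60 + Gulf (UAE/Qatar) 20 + Jordan 20 + Lebanon 65 + Morocco 15 + KSA 20 = 200. Centres: 5 + 2 + 1 + 6 + 2 + 3 = 19. Both stated totals are reproduced. The text above Table 3 still gives a larger target; I use 200, as in Table 3 and section 8.1.

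**2. Levels defined against levels in the shells.**

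| Variable | Levels defined | Rows in the shells | Defined, no row | Row, not in the study |
|---|---|---|---|---|
| Country (Shells 10, 11) | Egypt, Jordan, Lebanon, UAE, Qatar, Morocco, KSA | Algeria, Egypt, KSA, Kuwait, Lebanon, Morocco, UAE | Jordan, Qatar | Algeria, Kuwait |
| Sex (Shells 10, 11) | Male, Female | Female | Male | none |
| ECOG (Shells 12, 13) | 0 to 5 | 0, 1, 3, 4, 5 | 2 | none |

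The two country lists share five names, so together they hold 7 + 7 − 5 = 9 countries. That equals the stray count in Annex 1 and suggests a leftover from another country list, though the documents do not say so. Each mismatch appears identically in the first-line and second-line shell, so a PDF reading fault is unlikely.

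**3. Patients with no country row.** Let q be the number enrolled in Qatar. The share is (20 + q) / 200, taken over Shells 10 and 11 together; the split by line of therapy is not given. Table 3 does not divide the 20 Gulf patients between UAE and Qatar, so q is an assumption.

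- q = 0: 20/200 = 10%
- q = 10: 30/200 = 15%
- q = 19: 39/200 = 19.5%
- q = 20: 40/200 = 20%

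**4. Patients with no ECOG or sex row.** Neither number is in the documents. For scale only, an assumed ECOG 2 share of 5% to 15% would be 10 to 30 of 200 patients. I put no figure on men.

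**5. Effect on the percentages.** Let N be the table total, k the patients without a row, and a the count in a listed row.

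- Patients left unlisted: the rows add to (N − k)/N. For Jordan alone, 180/200 = 90%.
- Patients filed as missing: the Missing row rises by k/N. For Jordan alone, 20/200 = 10 percentage points.
- In both cases the listed percentage a/N is unchanged. It would rise, to a/(N − k), only if these patients were taken out of the denominator.

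**6. Whether the information survives elsewhere.** Shells 5, 17, 25, 33, 41, 57 and 65 have columns for all seven countries, so country counts can be recovered. No legible shell has a row for ECOG 2 or for men. Some shell pages are not legible in the text available, but the titles in SAP section 7 show none devoted to either. Shells 12 and 13 do count females in the menopausal-status block. The number of men follows by subtraction only if sex is never missing, and the Sex block has no Missing row with which to check that.

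**The case against.** The strongest reply is that these are clerical slips that a competent programmer would catch. The right countries appear in the SAP's design section, subgroup section and Annex 1 list, and a sequence of 0, 1, 3, 4, 5 is plainly a dropped row. The study is descriptive, no test or primary endpoint depends on these tables, and nothing changes in what is collected. This stands as an argument about severity. It does not remove the point, because the shells are the output specification for a stated objective and they disagree with the definitions they should implement. Nor can the country rows be excused as predating the country change: the SAP says it was built on protocol version 2.0 of 13 December 2021, and the amendment log dates the move to the seven countries to that same day.

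Several stronger readings are tempting, and the documents do not support them.

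- **Patients disappear from the report.** They do not. They remain in the total of each baseline table, and Jordan and Qatar appear in the by-country shells.
- **The cohort would look fitter.** That needs ECOG 2 patients removed from the denominator. Nothing in the SAP instructs this, and section 5 says missing data are no ground for exclusion from analysis.
- **Up to 40 patients lack a country row.** That ceiling needs every Gulf patient to be in Qatar and none in UAE, although both are study countries.
- **Men are a material omission.** Entry must follow the licensed indication, and the indications described in the protocol's background concern women, so there may be few men or none. Protocol section 10.6.1 mentions treated men, but as general pregnancy-exposure text it is weak evidence that men are expected.
- **ECOG 2 patients are under-represented in trials.** The documents give no source for this, so it forms no part of the point.

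**Conclusion.** The point holds as a defect in the output specification. Shells 10 to 13, followed literally, would leave recorded values without a row in three baseline variables. The documented size is Jordan's planned 20 of 200 patients (10%), plus a Qatar share that the protocol does not state, plus all ECOG 2 patients, whose number is not given. Men add to this only if any are enrolled. These figures assume that enrolment follows Protocol Table 3 and that the shells are programmed as written.

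The consequence is blocks that do not add to 100%, or an inflated Missing row. A reader should not infer biased percentages in the listed rows. The country distribution can be rebuilt from other tables; the ECOG 2 count cannot, unless the optional ECOG stratification is run. Primary endpoints are unaffected. This should be corrected before the tables are programmed, but it does not threaten the study.

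**What to change.** - **Shells 10 and 11, country:** replace the rows with the seven study countries.
- **Annex 1, Table 3, country:** change nine to seven.
- **Shells 12 and 13, ECOG:** add a row for grade 2. Removing the row for grade 5 (dead), which can hold no one at treatment initiation, is optional tidying.
- **Shells 10 and 11, sex:** add a Male row, and preferably a Missing row so that the block can be checked against the total.
- **Menopausal-status shells:** footnote the number of men, if any, who fall in neither column. SAP section 3.2 divides the full analysis set into subgroups, whereas Annex 1 defines menopausal status for females only.

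All of this is editing of SAP shells, using levels that Annex 1 already defines. It needs no new data and no change to any analysis.
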